12.6 Post-Infusion Follow-Up – Weeks 27-52

After Week 27, subjects will have assessments at Weeks 28, 30, 32, 34, 36, 40, 44, 48, 50, and 52. Visits between scheduled clinic visits may be performed by a mobile nursing (MN) professional at the subject's home or another suitable location (if the subject has given written informed consent to participate in MN visits), or at the site or approved lab facility as a shortened lab draw-only visit. The MN service or site will collect blood samples at these visits. For site lab draw-only visits, sites will contact the subject via phone call or e-mail to collect information regarding adverse events, changes to concomitant medications, bleeding episodes, and hemophilia therapy use. For MN visits, the service will collect this information. Unscheduled visits may also be conducted by MN as appropriate.

At these visits, the following assessments will be performed.

12.6.1 Each Visit (Weeks 28, 30, 32, 34, 36, 40, 44, 48, 50, and 52)

The following procedures will be performed at every visit (Week 26, 28, 30, 32, 34, 36, 40, 44, 48, 50, and 52):

- Assessment of Adverse Events and Concomitant Medications (including review of subject diary for bleeding and FVIII use)
- Liver Tests (refer to [Table 9.7.8.3.1](#))
 - LTs may be monitored more or less frequently (and in particular when ALT values are $>$ ULN or ≥ 1.5 x baseline value) based on discussion between the Medical Monitor and the Investigator and review of subject data, but LTs will be monitored at least twice weekly during periods when a subject's ALT is ≥ 3 x ULN.
- Samples for FVIII Assays
 - FVIII activity level (chromogenic substrate FVIII assay)
 - FVIII activity level (one-stage clotting FVIII assay)
 - FVIII coagulation activity exploratory assay
 - Chromogenic Nijmegen-Bethesda Assay for hFVIII inhibitor level
 - FVIII protein assay
- Exploratory CK18 and Grp78 assessment

12.6.2 Weeks 28, 32, 36, 40, 44, 48, and 52

At Weeks 28, 32, 36, 40, 44, 48, and 52, the following procedure will be performed:

- Brief physical examination (complete physical examination at Week 52)

12.6.3 Week 28, 36, 44, and 52

At Weeks 28, 36, 44, and 52, the following procedure will be performed:

- Plasma, PBMC, and RBC collection for exploratory biomarkers

12.6.4 Week 32

At Week 32, the following procedure will be performed:

- Testing for reactivation of hepatitis B and hepatitis C
 - Testing for reactivation of hepatitis B and hepatitis C only for subjects with a past medical history of hepatitis B or hepatitis C prior to study entry.

12.6.5 Weeks 32, 36, 40, 44, 48, and 52

At Weeks 32, 36, 40, 44, 48, and 52, the following procedure will be performed:

- Vital Signs

12.6.6 Weeks 32, 36, 44, and 52

At Weeks 32, 36, 44, and 52, the following procedures will be performed:

- Weight
- Blood chemistry, hematology, and coagulation tests (refer to [Table 9.7.8.2.1](#))
- PCR of vector DNA in blood, saliva, urine, semen, and stools
 - Sample testing to occur until at least 3 consecutive sample results below the limit of detection have been obtained.
- TGA assay

12.6.7 Week 36 and 52

At Weeks 36 and 52, the following procedures will be performed:

- Urine Tests (refer to [Table 9.7.8.2.1](#))
- Immunogenicity AAV5 TAb Assay
- AAV5 TI Assay
- hFVIII TAb
- IFNg ELISpot
- Complement Panel
- Serum for exploratory biomarkers

12.6.8 Week 52

At Week 52, the following procedure will be performed:

- Haemo-QoL-A assessment
- EQ-5D-5L
- WPAI+CIQ:HS
- PROBE

12.6.9 Week 52

At Week 52, the following optional procedure will be performed:

- Optional liver biopsy (refer to Section [12.9](#) for assessments related to liver biopsy)

12.7 Post-Infusion Follow-Up – Years 2-5

During Years 2-5, at applicable sites, certain study assessments may be performed by a mobile nursing (MN) professional at the patient's home or another suitable location, such as their school or office, to improve access and convenience for patients participating in the study. The Sponsor may select a healthcare company that will be responsible for providing MN services for participating sites (the MN vendor). The MN vendor is responsible for ensuring that all MN professionals are licensed, qualified, and in good standing, as per applicable regulations, and that appropriate background checks have been performed. If the investigator at a participating site determines that MN services are appropriate for a patient and the patient gives written informed consent to participate in MN visits, the MN network will communicate with the patient and the patient's site. MN visits will be allowed for the Q4W and Q6W visits during Years 2-5; the Q12W visits and End of Year visits during Years 2-5 will not be performed by an MN professional but will be done at the study site. Unscheduled visits may also be conducted by MN as appropriate.

Subjects who meet the definition of treatment failure to BMN 270 therapy after Week 52 may omit the Q4W and Q6W visits during Years 2-5, and must attend only the Q12W and End of Year visits. Such subjects following the abbreviated schedule who have not yet cleared vector shedding in semen must still provide samples Q4W (during Year 2) or Q6W (during Years 3-5) until vector shedding has been cleared, either by reporting to the site to provide samples or by providing those samples to a MN professional.

During Years 2-5 of Post-Infusion Follow-up, the following procedures will be completed:

12.7.1 Year 2 (Every 4 Weeks) or Years 3-5 (Every 6 Weeks)

During Years 2 (every 4 weeks \pm 2 weeks) or Years 3-5 (every 6 weeks \pm 2 weeks), the following procedures will be performed:

- Assessment of Adverse Events and Concomitant Medications (including review of subject diary for bleeding and FVIII use)
- Liver Tests (refer to [Table 9.7.8.3.1](#))
 - LTs may be monitored more or less frequently (and in particular when ALT values are $>$ ULN or ≥ 1.5 x baseline value) based on discussion between the Medical Monitor and the Investigator and review of subject data, but LTs will be monitored at least twice weekly during periods when a subject's ALT is ≥ 3 x ULN.
- FVIII Assays
 - FVIII activity level (chromogenic substrate FVIII assay)
 - FVIII activity level (one-stage clotting FVIII assay)
 - FVIII coagulation activity exploratory assay
 - Chromogenic Nijmegen-Bethesda Assay for hFVIII inhibitor level
 - If a subject tests positive in the cNBA during Years 3-5, a fresh sample should be collected within 4 weeks of the initial visit that had a positive result.
 - FVIII protein assay
- Exploratory CK18 and Grp78 assessment

12.7.2 Years 2-5 – Every 12 Weeks and End of Year Visits

During Years 2-5, subjects will be asked to return to the study site for visits at the following study weeks (\pm 2 weeks):

- Year 2 – Week 64, Week 76, Week 88, Week 104
- Year 3 – Week 116, Week 128, Week 140, Week 156
- Year 4 – Week 168, Week 180, Week 192, Week 208
- Year 5 – Week 220, Week 232, Week 244, Week 260 (final study visit)

For each of these years, the last study visit listed (Week 104, Week 156, Week 208, and Week 260) will serve as an End of Year visit.

At the every 12 week and End of Year visits, the following procedures will be performed:

- Physical examination
 - Complete physical examination will be performed at the End of Year visits; brief physical examination may be performed at other visits.
- Weight (at Week 76, Week 128, Week 180, Week 232, and End of Year visits only)
- Assessment of Adverse Events and Concomitant Medications (including review of subject diary for bleeding and FVIII use)
- Vital Signs
- Blood chemistry, hematology, and coagulation tests (refer to [Table 9.7.8.2.1](#)) (at Week 76, Week 128, Week 180, Week 232, and End of Year visits only)
- Urine Tests (refer to Table 9.7.8.2.1) (at Week 76, Week 128, Week 180, Week 232, and End of Year visits only)
- Liver Tests (refer to [Table 9.7.8.3.1](#))
 - LTs may be monitored more or less frequently (and in particular when ALT values are $>$ ULN or ≥ 1.5 x baseline value) based on discussion between the Medical Monitor and the Investigator and review of subject data, but LTs will be monitored at least twice weekly during periods when a subject's ALT is ≥ 3 x ULN.
- FVIII Assays
 - FVIII activity level (chromogenic substrate FVIII assay)
 - FVIII activity level (one-stage clotting FVIII assay)
 - FVIII coagulation activity exploratory assay
 - Chromogenic Nijmegen-Bethesda Assay for hFVIII inhibitor level
 - If a subject tests positive in the cNBA during Years 3-5, a fresh sample should be collected within 4 weeks of the initial visit that had a positive result.
 - FVIII protein assay
- Immunogenicity AAV5 TAb Assay (at End of Year visits only)
- AAV5 TI Assay (at End of Year visits only)
- hFVIII TAb
- Interferon gamma (IFNg) ELISpot (at Week 76, Week 128, Week 180, Week 232, and End of Year visits only)
- Plasma, PBMC, and RBC collection for exploratory biomarkers
- Serum for exploratory biomarkers

- Exploratory CK18 and Grp78 assessment
- TGA Assay (at End of Year visits only)
- Haemo-QoL-A assessment (at Week 76, Week 128, Week 180, Week 232, and End of Year visits only)
- EQ-5D-5L (at Week 76, Week 128, Week 180, Week 232, and End of Year visits only)
- WPAI+CIQ:HS (at Week 76, Week 128, Week 180, Week 232, and End of Year visits only)
- PROBE (at Week 76, Week 128, Week 180, Week 232, and End of Year visits only)
- PCR of vector DNA in blood, saliva, urine, semen, and stools (if required)
 - Sample testing during Years 2-5 is not required if at least 3 consecutive samples are below the limit of detection during the Post-Infusion Follow-Up period in Weeks 1-52. Subjects who have not had 3 consecutive semen samples below the limit of detection by Week 52 should continue to have PCR testing of semen every 4 weeks (during Year 2) or every 6 weeks (during Years 3-5) until 3 consecutive samples below the limit of detection are documented (or upon consultation between the Investigator and Medical Monitor).
- Optional liver biopsy (Years 2-5) (refer to Section 12.9 for assessments related to liver biopsy)

12.8 Early Termination Visit

If a subject leaves the study prior to the Week 260 visit, the subject will be asked to return to the study site and complete an ETV. The Early Termination Visit (ETV) will occur on the date the subject withdraws from the study, even if the date does not correspond to a protocol-specific visit. At the ETV, as many of the following assessments as possible should be done:

- Complete physical examination
- Weight
- Assessment of Adverse Events and Concomitant Medications (including review of subject diary for bleeding and FVIII use)
- Vital Signs
- Blood chemistry, hematology, and coagulation tests (refer to [Table 9.7.8.2.1](#))
- Urine Tests (refer to [Table 9.7.8.2.1](#))
- Liver Tests (refer to [Table 9.7.8.3.1](#))

- FVIII Assays
 - FVIII activity level (chromogenic substrate FVIII assay)
 - FVIII activity level (one-stage clotting FVIII assay)
 - FVIII coagulation activity exploratory assay
 - Chromogenic Nijmegen-Bethesda Assay for hFVIII inhibitor level
 - FVIII protein assay
- PCR of vector DNA in blood, saliva, urine, semen, and stools (if required)
- Immunogenicity AAV5 TAb Assay
- AAV5 TI Assay
- hFVIII TAb
- IFNg ELISpot
- Plasma, PBMC, and RBC collection for exploratory biomarkers
- Serum for exploratory biomarkers
- Exploratory CK18 and Grp78 assessment
- TGA Assay
- Haemo-QoL-A assessment
- EQ-5D-5L
- WPAI+CIQ:HS
- PROBE

12.9 Optional Liver Biopsy

Details on required procedures for the optional liver biopsy are outlined in [Table 9.1.5](#). Subjects may be asked to provide a liver biopsy around Week 26, Week 52, and during the Years 2-5 period post-BMN 270 infusion.

Subjects consenting to participate to the optional liver biopsy will undergo pre-biopsy assessments at least 28 days before the procedure, as follows:

- Liver ultrasound (subject should fast at least 8 hours prior to ultrasound)
- Physical examination
- Hematology, coagulation, chemistry assessments
- Liver tests
- FibroScan

Subjects consenting to participate to the optional liver biopsy will undergo pre-biopsy assessments at least 7 days before the procedure, as follows:

- FVIII activity level assessment (central and local)
- Exploratory CK18 and Grp78 assessment
- Pre-biopsy consultation (with hepatologist and/or radiologist)

On the day of the biopsy, brief physical examination and liver and blood tests should be performed before the procedure (including hematology, coagulation, and chemistry). FVIII activity assessment should also be performed to ensure the subject has sufficient FVIII activity to protect against procedure-related bleeding (as discussed above). LT assessment and a whole blood draw for PBMC collection should be performed on the biopsy day or \pm 1 week from the biopsy day.

The optional liver biopsy should be performed in the morning if feasible, and the biopsy procedure and follow-up care should be done according to the local standard of care.

Additional details for handling the biopsy specimens are provided in the Study Reference Manual.

Following completion of the biopsy, the subject should remain under observation in the clinic for at least 4-6 hours. Overnight post-procedure observation may be done at the investigator's discretion and/or according to local guidelines.

12.10 End of Study

The study will end after the last subject yet to complete the Week 260 visit does so, has transferred to another BMN 270 study, is withdrawn from the study, or discontinues from the study. BioMarin reserves the right to discontinue the study any time for clinical or administrative reasons and to discontinue participation of an individual Investigator or site for clinical or administrative reasons, including, but not limited to, poor enrollment or noncompliance with procedures of the protocol or GCP. In addition, the study may be terminated if, in the opinion of BioMarin, the safety of the study subjects may be compromised.

13 DATA QUALITY ASSURANCE

BioMarin personnel or designees will visit the study site prior to initiation of the study to review with the site personnel information about the IP, protocol and other regulatory document requirements, source document requirements, eCRFs, monitoring requirements, and procedures for reporting AEs, including SAEs.

At visits during and after the study, a CRA will monitor the site for compliance with regulatory documentation, with a focus on accurate and complete recording of data on eCRFs from source documents, adherence to protocol, randomization (if applicable), SAE reporting and drug accountability records.

Sites will enter study data into eCRFs into the study EDC system. Data Quality Control will be performed by BioMarin Clinical Data Management or designee through implementation of quality control checks specified in the study data management plan and edit check specifications.

14 STATISTICAL METHODS AND DETERMINATION OF SAMPLE SIZE

14.1 Statistical and Analytical Plans

The statistical analysis plan (SAP) will provide additional details on the planned statistical analyses. Unless otherwise stated, all analyses will be performed using SAS.

14.1.1 Interim Analyses

No formal interim analysis is planned. Informal analyses (ie, no hypothesis testing) may be performed at different timepoints to assess efficacy and safety over time. The primary efficacy endpoint for such analyses involves hFVIII activity, as measured by chromogenic substrate assay, and is defined as median FVIII activity during a specific 4-week time interval post-BMN 270 infusion.

14.1.2 Procedures for Accounting for Missing, Unused and Spurious Data

Because the completeness of the data affects the integrity and accuracy of the final study analysis, every effort should be made to ensure complete, accurate, and timely data collection and, therefore, avoid missing data.

Missing data imputation and sensitivity analyses to assess the impact of missing data on the primary and secondary efficacy endpoints analyses are described in the following sections. Additional details regarding the handling of missing data will be provided in the SAP.

14.2 Primary Efficacy Endpoint

For the primary efficacy endpoint at Week 52 (ie, the change in the hFVIII activity during Weeks 49-52 post-BMN 270 infusion from baseline, as measured by chromogenic substrate assay), a one-sample t-test will be used to test the null hypothesis that the change is 0 or less against the alternative hypothesis that the change is greater than 0 at the 1-sided significance level of 0.025 (or equivalently, at the 2-sided significance level of 0.05). Baseline value of 1 IU/dL (eligible subjects must have residual FVIII levels \leq 1 IU/dL as evidenced by medical history) will be used in the calculation of change from baseline since all the subjects will be on prophylactic hemophilia therapy prior to BMN 270 infusion where the FVIII activity level cannot be reliably measured. Descriptive summaries of the proportions of subjects whose hFVIII activity during Weeks 49-52 is greater than or equal to select thresholds, such as 5, 15, 25, 30, and 40 IU/dL, and the confidence intervals of the proportions will also be provided.

For a subject with a missing value of the primary endpoint, the median value in the subject's last 4-week window containing a valid observation will be used. Additional analyses will be

conducted to examine the sensitivity of the results to the handling of missing data, including analysis using observed cases, and a mixed model for repeated measures (MMRM) approach. Further detail will be provided in the SAP.

The analyses for the primary endpoint will be performed using the analysis populations as defined in Section 14.9.

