Treatment of severe HA includes intravenous injection of plasma-derived or recombinant human FVIII protein (rhFVIII) concentrates, both as prophylaxis 2-3 times per week, and at the time of a bleed, to prevent or control bleeding episodes, respectively and/or subcutaneous injection of a bi-specific monoclonal antibody, emicizumab, as prophylaxis 1-4 times per month. The half-life for FVIII (12 to 18 hours for most approved products) necessitates frequent infusions, and although a major advance in the treatment of HA, it remains common for severe HA patients to continue to have multiple bleeding events on prophylactic therapy (median annualized bleeding rate [ABR] of 1-4 with prophylaxis treatment in a recently published retrospective observational study and between 1-2 in 6 prospective FVIII interventional studies) and on-demand-only therapy (median ABR of 4.5-18 in a recently published retrospective study and between 20-60 in		

NAME OF COMPANY	SUMMARY TABLE	FOR NATIONAL AUTHORITY USE ONLY:
BioMarin Pharmaceutical Inc. [name]	Referring to Part of the Dossier:	
NAME OF FINISHED PRODUCT: BMN 270	Volume:	
NAME OF ACTIVE INGREDIENT: AAV5-hFVIII-SQ	Page:	

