
 1. Any condition that, in the opinion of the Investigator or a hepatologist or radiologist, would make liver biopsy contraindicated. This includes (but is not limited to): abnormalities detected on liver ultrasound performed within 28 days of procedure or prior liver ultrasound result within 90 days that would preclude safe performance of the biopsy. 		

NAME OF COMPANY	SUMMARY TABLE	FOR NATIONAL AUTHORITY USE ONLY:
BioMarin Pharmaceutical Inc. [name]	Referring to Part of the Dossier: Volume:	
NAME OF FINISHED PRODUCT: BMN 270	Page:	
NAME OF ACTIVE INGREDIENT: AAV5-hFVIII-SQ	Reference:	
INVESTIGATIONAL PRODUCT(S), DOSE, ROUTE AND REGIMEN: Each subject will receive a single intravenous infusion of BMN 270 at 6E13 vg/kg. The volume of infusion will depend on the subject's weight		
REFERENCE THERAPY(IES), DOSE, ROUTE AND REGIMEN: No reference therapy will be evaluated in this study.		
DURATION OF TREATMENT: BMN 270 is given as a single dose by intravenous infusion.		
CRITERIA FOR EVALUATION: Efficacy: Primary efficacy endpoint: 
 Change of the hFVIII activity, as measured by chromogenic substrate assay, during Weeks 49-52 post-BMN 270 infusion from baseline. Each subject's hFVIII activity during Weeks 49-52 is defined as the median of the values obtained during this 4-week window. Values for hFVIII activity will be excluded if obtained within 72 hours since the last infusion of exogenous FVIII protein concentrates. Secondary efficacy endpoints: 
 Change from baseline in the annualized utilization (IU/kg/year) and infusion rate (number/year) of exogenous FVIII replacement therapy during Week 5 to Week 52 post-BMN 270 infusion, for subjects receiving FVIII prophylaxis during the 12 months prior to study entry or change from baseline in the annualized utilization (mg/kg/year) of emicizumab during Week 27 to Week 52 post-BMN 270 infusion for subjects receiving prior emicizumab prophylaxis. Change from baseline in the annualized number of bleeding episodes requiring exogenous FVIII replacement treatment (annualized bleeding rate, ABR) during Week 5 to Week 52 post-BMN 270 infusion for subjects receiving prior FVIII prophylaxis, or Week 27 to Week 52 post-BMN 270 infusion for subjects receiving prior emicizumab prophylaxis Change from baseline in the total score of Haemo-QoL-A at Week 52 post-BMN 270 infusion 		

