7.3.1 Optional Liver Biopsy Rationale

The usual pattern of response in hFVIII activity observed so far after administration of BMN 270 demonstrates peak expression levels during the first 6-12 months post-treatment followed by a decline to a steady-state level of expression thereafter. One of the explanations may lie in the kinetics of vector genome processing, which involves a series of steps such as DNA degradation and repair, annealing, and circularization that can result in the formation of stable, double-stranded, circularized transgene DNA forms. It is these circularized DNA species that are thought to be associated with long-term, persistent expression of the gene product in target cells. Examination of transduced hepatocytes from subjects treated with BMN 270 in the 270-303 study will help to establish whether DNA circularization may occur and could account for the long-term hFVIII expression observed in humans.

Additionally, health of the liver after gene transduction has been monitored indirectly by periodic assessments of hepatic enzymes released into the blood stream. Transient, post-treatment elevations in ALT levels have been observed in the majority of subjects, as well as inter-subject variability in post-therapy FVIII activity levels. Neither the reasons for nor the significance of the ALT elevations or the variations in response to FVIII gene therapy are known. Moreover, the effects of BMN 270 on hepatic tissue structure and function are also currently unknown. Finally, a call to incorporate liver biopsy sub-studies into gene therapy trials for hemophilia has been issued by medical and scientific leaders in the field to help illuminate these and other questions ([National Hemophilia Foundation, 2019](#)).

The purpose of this exploratory sub-study is to provide a better understanding of the long-term gene expression related to genome circularization, health of the liver, and variation in FVIII activity levels observed after gene therapy with BMN 270. With use of prophylactic corticosteroids, it is believed that there will be stable hepatic function and FVIII activity expression, with tolerance of prophylactic corticosteroid therapy and no change to the risk of thromboembolism. This sub-study aims to evaluate the effect on the liver by performing liver biopsies at approximately Week 26, Week 52, and/or during Years 2-5.

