9.7.2 Primary Efficacy Variables

9.7.2.1 FVIII Activity

The primary efficacy variable is change of the hFVIII activity, as measured by chromogenic substrate assay during Weeks 49-52 post-BMN 270 infusion from baseline.

If a subject has used FVIII within 72 hours of a measurement day, all efforts should be made to obtain FVIII activity measurements when a 72-hour interval without FVIII use is achieved; The 72-hour wash-out period is only intended for subjects who have achieved FVIII ≥ 5 IU/dL at the end of 16 weeks after BMN 270 infusion and who have not resumed FVIII replacement therapy.

In the event of an FVIII activity level decline during the study:

- If FVIII activity has declined at least 20% from the peak but less than 35% and has declined for at least 2 consecutive assessments, FVIII activity and LTs should be repeated every 7 days until FVIII activity is stable or increasing
- If FVIII activity has declined $\geq 35\%$ from the peak and has declined for at least 2 consecutive assessments, FVIII activity and LTs should be repeated every 72 hours until FVIII activity is stable or increasing

Note that fluctuations in FVIII activity are common, and if no clear trend indicating a decline in FVIII activity is observed, then this additional testing may be deferred (upon consultation between the Investigator and the Medical Monitor) until either a more clear trend of decline has been demonstrated or until the FVIII activity levels stabilize or increase.

Details on collecting FVIII activity samples are included in the Laboratory Manual.

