9.7.3 Secondary Efficacy Variables

9.7.3.1 Factor VIII Replacement Therapy/Bleeding Episodes

Secondary efficacy variables include:

- Change in the annualized utilization (IU/kg/year) and infusion (number/year) rates of exogenous FVIII replacement therapy during Week 5 to Week 52 post-BMN 270 infusion from the baseline number and utilization of exogenous FVIII replacement therapy, for subjects receiving FVIII prophylaxis during the 12 months prior to study entry, or change in administration of exogenous FVIII replacement therapy Week 27 to Week 52 post-BMN 270 infusion for subjects receiving prior emicizumab prophylaxis.
- Change in the annualized number of bleeding episodes requiring exogenous FVIII replacement treatment (annualized bleeding rate, ABR) during Week 5 to Week 52 post-BMN 270 infusion for subjects receiving prior FVIII prophylaxis, or Week 27 to Week 52 post-BMN 270 infusion for subjects receiving prior emicizumab prophylaxis, from the baseline ABR during the 12 months prior to study entry.

Subjects must have high quality documented historical data available concerning previous bleeding episodes and hemophilia treatment over the previous 12 months in order to be eligible to enroll in the study. During the study, subjects will be asked at each study visit to

report the use of factor replacement therapy and the number of bleeding episodes since the previous visit. This information will be captured on the subject's diary or other subject records.

Subjects are strongly encouraged to immediately consult Investigator for guidance regarding exogenous FVIII administration for suspected bleeds or bleeding episodes within the first 30 days post-BMN 270 infusion.

In subjects who experience recurrent bleeding episodes, the Investigator and Medical Monitor will discuss whether to resume prior FVIII prophylaxis or use of emicizumab.

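### The primary endpoint can score a subject back on FVIII prophylaxis with a value from before resumption, and neither named sensitivity analysis tests this

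*Protocol*

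**What the plan says.** Four provisions meet here.

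- **Endpoint.** In the Synopsis, each subject's activity in Weeks 49-52 "is defined as the median of the values obtained during this 4-week window". The same paragraph adds: "Values for hFVIII activity will be excluded if obtained within 72 hours since the last infusion of exogenous FVIII protein concentrates".
- **Wash-out.** Section 9.7.2.1 asks sites to try for a sample after 72 hours without FVIII, but limits whom this is for: "The 72-hour wash-out period is only intended for subjects who have achieved" at least 5 IU/dL "at the end of 16 weeks after BMN 270 infusion and who have not resumed FVIII replacement therapy".
- **Missing endpoint.** Under Section 14.2, "the median value in the subject's last 4-week window containing a valid observation will be used". The sensitivity analyses it names are observed cases and an MMRM, with further detail left to the SAP.
- **Resumption.** Section 9.1 foresees a return to FVIII prophylaxis after recurring bleeds. It lists inability to stay off prophylaxis because of joint bleeding as one of two forms of treatment failure. The Synopsis describes FVIII as given "both as prophylaxis 2-3 times per week".

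Section 14.2 is read from the protocol of 28 February 2020. The Amendment 1 text at hand stops in Section 10.2.1. None of the changes it lists names this rule, and its Synopsis keeps the 72-hour exclusion.

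**The concern.** Excluding values contaminated by infused FVIII is sound. The difficulty is what takes their place. For a subject back on regular FVIII, the endpoint is missing because the subject resumed treatment. The wash-out provision does not seek a clean value from that subject, and the imputation reaches back to a window that will usually precede the regular infusions. A protocol-defined failure can then contribute an earlier, possibly higher, value to the mean change and count as a success at the 5 IU/dL threshold, or at higher ones.

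The named sensitivity analyses do not probe this. Observed cases leaves these subjects out. MMRM predicts them from their earlier values under missing at random, whereas here the missingness follows from the failure. Neither gives them a failure value.

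The estimated mean and the threshold proportions are at stake. In a single-arm trial tested against a change of zero or less, these are the informative results.

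**Working it through.** **Inputs.** n = 16, effect size 0.8, one-sample t-test, one-sided 0.025, stated power 85% (Section 14.8). Baseline 1 IU/dL for every subject (Section 14.2). Visits at Weeks 48, 50 and 52 (Section 12.6), so nominally two samples fall in Weeks 49-52. Withdrawn subjects are not replaced (Section 9.3.4). The number of resumed subjects, k, and their last valid window median, v, are not in the documents and are assumed.

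**1. The plan's own figure.** Noncentral t with df = 15 and noncentrality 0.8 × √16 = 3.2 gives power 84.8%, which reproduces 85%.

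**2. How much of the window survives the exclusion.**
- Three infusions a week, at gaps of 48, 48 and 72 h: no time lies more than 72 h after an infusion, so no value is valid.
- Two a week, at gaps of 72 and 96 h: 96 − 72 = 24 valid hours out of 168, or 1/7 = 14%. Even spacing gives the same share: (84 − 72)/84 = 1/7.

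One valid value is enough to avoid imputation, so at two infusions a week the endpoint is often but not always missing.

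**3. What replaces it.** With no valid Weeks 49-52 value, Section 14.2 moves back to the latest window that has one. While infusions run at three a week there is none, so the carried window predates regular infusions.

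**4. Shift in the mean change.** If the subject is carried at v and would otherwise be scored at 1 IU/dL, shift = k × (v − 1)/16, in IU/dL:

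| k | v = 5 | v = 10 | v = 20 | v = 30 |
|---|---|---|---|---|
| 1 | 0.25 | 0.56 | 1.19 | 1.81 |
| 2 | 0.50 | 1.13 | 2.38 | 3.63 |
| 3 | 0.75 | 1.69 | 3.56 | 5.44 |

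If true activity is 3 rather than 1 IU/dL, one subject shifts the mean by (10 − 3)/16 = 0.44 or (20 − 3)/16 = 1.06. If the carried window had already fallen to 3 and the truth is 1, the shift is only 2/16 = 0.125.

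**5. Shift in the proportion at or above 5 IU/dL.** Each subject carried at 5 or more adds 1/16 = 6.25 percentage points. With k = 2 and all others above 5, the report reads 16/16 (exact 95% interval 79.4% to 100%) instead of 14/16 = 87.5% (61.7% to 98.4%).

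**6. Power if these subjects are scored as change 0.** Simulation with the remaining subjects normal at effect size 0.8 gives about 82%, 79% and 75% for k = 1, 2, 3. Carrying the same subjects at 15 IU/dL, with the others at an assumed mean change of 20, gives about 86%, 87% and 88%.

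**The case against.** **The last valid window may already be low.** FVIII is sampled weekly to Week 26 and every two to four weeks afterwards. Section 9.7.2.1 calls for closer testing once activity falls 20% or 35% from its peak, and resumption follows recurring bleeds. This stands: the documents support a direction of bias, not a size.

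**Scoring at 1 IU/dL has its own bias.** The primary variable is activity, not treatment success, and the joint-bleeding form of failure sets no FVIII level. A subject who resumes while still expressing some FVIII would be understated. This also stands, and is why a named sensitivity analysis is an acceptable minimum.

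**Failure is visible elsewhere, and the SAP may say more.** Resumed FVIII counts in the utilization and infusion-rate endpoints for subjects previously on FVIII, and the list of sensitivity analyses in 14.2 is not closed. True, but the carry-forward rule is fixed in the protocol, and other endpoints do not correct the primary mean or proportions.

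**Two wider readings are not supported.**
- A reader might infer that carry-forward inflates every missing subject because expression declines. Section 7.3.1 says the response "demonstrates peak expression levels during the first 6-12 months post-treatment followed by a decline to a steady-state level of expression thereafter". Weeks 49-52 close month 12, so the described decline comes afterwards, and an early window could even precede the peak.
- A reader might infer that values on resumed emicizumab are invalid, since Section 9.7.3.1 lets the Investigator and Medical Monitor "discuss whether to resume prior FVIII prophylaxis or use of emicizumab". The remark in 14.2 about unreliable measurement on prophylaxis justifies the fixed pre-infusion baseline only. Nothing in the document shows that post-infusion values on emicizumab are distorted, and they are neither excluded nor carried forward.

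**Conclusion.** The point holds for subjects who are back on regular FVIII prophylaxis and have no valid Weeks 49-52 value. For them the primary analysis typically uses a pre-resumption window, and neither named sensitivity analysis treats them as failures.

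The likely effect is upward: (v − 1)/16 IU/dL per subject on the mean, and 6.25 points on the 5 IU/dL proportion when v is at least 5. Both figures rest on assumed v, on n = 16 and on true activity near 1 IU/dL. The document gives no failure rate.

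A reader might infer that the primary test is in danger. That is unlikely: the null is a change of zero or less, earlier studies reported levels above 15 IU/dL, and the protocol calls its effect size conservative. Severity is moderate. Confidence in the current wording is limited because Section 14 of Amendment 1 is not at hand.

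**What to change.** In Section 14.2 (and the SAP), for a subject who has resumed FVIII prophylaxis and has no valid Weeks 49-52 value:

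1. Do not carry forward a pre-resumption window. Set activity to the protocol's baseline of 1 IU/dL, which means a change of 0 and a value below every threshold.
2. Apply this in the primary analysis or, at minimum, in a named sensitivity analysis covering both the mean change and the threshold proportions.
3. Report how many subjects are affected.
4. Keep any valid Weeks 49-52 value as it is. Keep the last-window rule for other missing data and, for these subjects, as the alternative analysis.

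The no-benefit convention already exists in Section 14.3, where a missing change in utilization or infusion rate is set to 0.

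The cost is wording only, with no change to conduct. The estimate becomes slightly less favourable and may understate subjects with residual expression. If the rule is primary, power at the design effect size falls from about 85% to about 82%, 79% or 75% with one, two or three such subjects.
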